## **9.0 STUDY-SPECIFIC PROCEDURES**

### **9.1 Cognitive Evaluation Instruments Administered to the Participant**

Objective tests of cognitive function will include tests comprising the PACC5 (MMSE, Story Recall, the Rey Auditory Verbal Learning Test, Verbal Fluency), the CDR, and the ADAS-Cog14.

### **9.2 Clinical and Functional Evaluations**

#### **9.2.1 Quick Dementia Rating System (QDRS)**

The QDRS (Galvin, 2015) is a clinical scale that rates the severity of dementia as absent, questionable, mild, moderate, or severe (CDR score of 0, 0.5, 1, 2, or 3, respectively). The score assesses six domains: memory, orientation, judgment and problem solving, community affairs, home and hobbies, and personal care. At Screening the QDRS global score will be used for eligibility purposes. For all other administrations, the 6 domain scores will be summed to get the QDRS Sum of Boxes (SB) score.

#### **9.2.2 Activities of Daily Living Scale for MCI/ADL-MCI**

The ADL-MCI is an activities of daily living questionnaire aimed at detecting functional decline. In a structured interview format, informants are queried as to whether participants attempted each item in the inventory during the prior 4 weeks and their level of performance. The ADL-MCI scale discriminates well between normal controls and patients with mild AD or MCI. It has good test-retest

reliability. The questions focus predominantly on instrumental activities of daily living scales (e.g. shopping, preparing meals, using household appliances, keeping appointments, reading).

**9.2.3. PROMIS Sleep Disturbance and Sleep-Related Impairment Questionnaires (Short Form).**  
These 8-item forms ask participants to rate quality of sleep on a 5-point scale.

**9.2.4 Patient Health Questionnaire-9 (PHQ-9).**  
This widely-used 9 item questionnaire assesses depression.

**9.2.5 General Anxiety Disorder Scale (GAD-7)**  
This widely-used 7-item questionnaire assesses anxiety.

## **10.0 STUDY METHODS**

### **10.1 Safety Assessments**

At each study visit, all participants will undergo a nasal examination and any occurrence of adverse events will be reviewed and documented; concomitant medications will be recorded as well. In addition, 24 hours after the Lumbar Puncture, each study participant, or a person designated to speak for them will be contacted by phone to confirm the participant's well-being and queried about any new adverse events. All adverse events will be reported to the study MD for review.

### **10.2 Physical and Neurological Examination**

A brief physical examination will be performed by a medically qualified professional at the screening visit. A review of the major body systems will be performed for example: skin, head/ears/eyes/nose/throat (HEENT), cardiovascular, pulmonary, abdomen, musculoskeletal, neurological, and gastrointestinal. Assessments of height (Screening visit only), weight, and vital signs (systolic and diastolic blood pressure, pulse, temperature, and respiration) are included. Neurological examination will include an assessment of cranial nerves, strength, coordination, reflexes, sensation, tremor and gait at every study visit. A nasal examination will also be performed. The examination will assess irritation or other abnormalities of the nares.

### **10.3 Electrocardiogram (ECG)**

A resting ECG will be performed at Screening visit. The ECG report will be reviewed, signed, and dated by the study clinician. Those with clinically significant ECG findings will be referred for follow-up as deemed appropriate by the investigator and may be excluded from the study.

### **10.4 Clinical Laboratory Evaluations**

All routine laboratory samples will be analyzed by Laboratory Corporation of America (Labcorp). Lab reports will be reviewed, signed and dated by the study clinician. If a value is outside of the laboratory's normal range, the clinician will indicate if it is clinically significant or not. If clinically significant, lab tests may need to be repeated and follow up with the participant's PCP should occur.

### **10.5 Actigraphy**

The Empatica E4 device (<https://www.empatica.com/en-eu/research/e4/>) will be used to assess sleep quality. It uses an accelerometer to assess physical activity and heart rate variability from which a sleep quality index is calculated.

### **10.6 Continuous Glucose Monitoring**

The Abbott Freestyle Libre Pro is a continuous glucose monitor (CGM) system; a thin filament sensor the size of a quarter covered with a waterproof patch will be placed by a clinician or qualified study team member on the back of the participant's upper arm and worn for 7 days, then removed by the participant. The sensor records and uploads glucose data every 15 min. A report of average glucose

levels and number of hyperglycemic/hypoglycemic episodes can be linked to events such as meals, sleep, and activity. Participants will be assessed over a 1-week period.

## **11.0 BIOMARKER STUDIES**

### **11.1 CSF**

All CSF samples will be collected in the morning before breakfast and after an overnight fast. Participants who are taking anticoagulants cannot be enrolled unless documentation is received from the prescribing clinician that the anticoagulant medication can be held before the LP visits, and is approved by a study clinician. Based on clinician judgment and depending on the clinical indication, it may be suitable to discontinue participants from their anti-platelet agent (e.g., aspirin, Plavix, NSAIDs) for 5-7 days prior to lumbar puncture and until at least 24 hours after lumbar puncture. It is not required that participants be discontinued from their anti-platelet agent in order to screen and enroll in the study.

A minimal total volume of CSF (~25 ml) will be required for this study. To clear any blood from minor trauma associated with needle insertion, the first 1-2 mL of CSF are discarded (or more if needed). Collected CSF is aliquoted into sterile microtubes. Approximately 2ml of CSF or volume per local laboratory requirements will be sent at ambient temperature to the CRU laboratory for protein, glucose and cell count. CSF will be immediately frozen upright on dry ice for at least 20 minutes then stored at -70 until analysis.

CSF samples will be used to measure levels of insulin, A $\beta$ 42, A $\beta$ 40, total tau, and phospho-tau181. Assays will be performed by the Wake Forest ADRC Biomarker Service. CSF samples will also be frozen and stored for future analysis of putative biomarkers.

### **11.2 Blood Collection at Lumbar Puncture Visits**

All samples will be collected in the morning before breakfast and after a minimum 8-hour overnight fast. Blood samples (26 mL) will be collected before and after insulin administration. Blood will be processed for fasting plasma insulin and glucose. Additional blood for plasma and serum will be processed and banked.

### **11.3 Genetic Samples, Storage and Future Use**

DNA will be extracted from participant blood samples and will be analyzed for ApoE genotyping. ApoE genotyping will be used as a weighting factor for the minimization strategy during randomization. This will allow secondary analyses of data on the impact of the ApoE genotype on putative biomarkers of AD, clinical outcome measures, and adverse events. ApoE genotyping will be performed by [name] under the auspices of the ADRC Biomarker service using established protocols.

## **12.0 STATISTICAL PLAN**

Statistical analyses will be conducted by the ADRC Biostatistics Core. To address the Primary Aim, number of treatment-related SAEs will be subjected to a repeated measures analysis of variance with group and time as the repeated measures. Secondary analyses will examine the effect of diagnostic status (cognitively normal vs. MCI/AD). Secondary analyses will also examine treatment-related differences for other CSF and plasma biomarkers, cognitive scores, and whole brain cerebral blood flow.

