PRIMARY OBJECTIVE	We will test the hypothesis that 1 month of treatment with INI (40 IU q.i.d.), with the SGLT2i empagliflozin (empa; 10 mg q.d.), and with combined insulin plus empagliflozin (INI+empa) will result in safety profiles (number of treatment-related serious adverse events/primary outcome) that are similar to placebo.
SECONDARY OBJECTIVES	We will determine the effects of singular and combined therapy on AD cerebrospinal fluid biomarkers, cerebral blood flow (CBF) and cognition.
PRIMARY OUTCOME MEASURE	Number of treatment-related serious adverse events
SECONDARY OUTCOME MEASURES	PACC5, ADAS-Cog14, CSF A $\beta$ 40, A $\beta$ 42, total tau, and phospho-tau 181, whole brain CBF
STUDY DESIGN	Single-site, double-blind study
SAMPLE SIZE	n=60
SUMMARY OF KEY ELIGIBILITY CRITERIA	
 
Cognitively normal with positive amyloid (amyloid PET SUVR>1.21, CSF A<math>\beta</math>42<600 pg/ml)
 
Diagnosis of amnestic mild cognitive impairment (MCI) or early AD (CDR 0.5 or 1, MMSE>21)
 
Age: 55 to 85 years (inclusive)
 

DRUG DOSAGE & FORMULATION	40 International Units Humulin® R U-100 (Eli Lilly, Inc.) q.i.d.; empagliflozin (10 mg q.d.)
DURATION OF PARTICIPATION	8 weeks (4 weeks on active treatment)
PLACEBO	Insulin diluent (Eli Lilly, Inc.); cellulose capsule

ROUTE OF ADMINISTRATION	Intranasal (insulin); oral (empagliflozin)
PROCEDURES	Physical and neurological exam, nasal examination, cognitive testing, magnetic resonance imaging (MRI), continuous glucose monitoring, actigraphic sleep assessment, lumbar puncture, vitals, clinical labs, CSF and blood analysis and banking and APOE genotyping.

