### 3.2 Procedures

Participants were randomized to receive 10 International Units INI bid for a total daily dose of 20 International Units INI (n=36), 20 International Units INI bid for a total dose of 40 International Units (n=38) or placebo (saline bid, n=30) for 4 months. Participants were stratified by APOE- $\epsilon$ 4 carriage. Saline or insulin (Novolin R, Novo) was administered after breakfast and dinner with ViaNaseTM, an intranasal delivery system (Craft, Baker et al. 2012). Parallel versions of the cognitive protocol were administered at baseline, and months 2 and 4 of treatment. Co-primary outcome measures were delayed story recall and the DSRS which had previously demonstrated beneficial effects of insulin (Reger, Watson et al. 2008). Secondary measures included the AD Assessment Scale for Cognition (ADAS-Cog) (Reger, Watson et al. 2008), a test comprised of measures of memory, orientation, and language, with higher scores reflecting impairment ranging from 0 (best) to 70 (worst), and the ADCS-Activities of Daily Living scale (ADCS-ADL) (Galasko, Bennett et al. 1997). Baseline and post-treatment fasting CSF was analyzed for A $\beta$ 42 and tau with multi-parameter bead-based immunoassay INNO-BIA AlzBio3 (Innogenetics NV). Resting PET images were obtained using a GE Advance PET scanner (GE Medical Systems, Milwaukee, WI) using a previously described protocol (Baker, Cross et al. 2011).

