### 3.8 Safety and Compliance

No treatment-related serious adverse events (SAEs) occurred during the study; most adverse events (AEs) were minor, such as mild rhinitis. AEs with an occurrence of >5% in any group are listed in Table 3. The total AE mean was higher for the low dose group compared with placebo (low dose mean total AEs with standard error=1.44±0.20, placebo =0.80±.22, p=0.04), with a similar trend for the high dose and placebo group comparison (high dose mean total AEs =1.21±0.16, placebo =0.80±.22, p=0.10). Mean compliance (number of completed doses) ranged from 95-97% and did not differ across groups.

**Table 3 | Total number of adverse events and percent of sample for all events occurring for at least 5% of the participants in any treatment group.**

	Placebo	Low Insulin	High Insulin
Total AEs	27/56.7%	55* /72.2%	51+ /68.4%
Dizziness	3/10%	3/8.3%	5/13.2%
Headache	1/3.3%	4/8.3%	2/5.3%
Nose bleed	0/0.0%	6/8.3%	3/2.6%
Rhinitis	1/3.3%	8/16.7%	4/7.9%
URI	2/6.7%	2/5.6%	1/2.6%
Fall	2/6.7%	1/2.8%	1/2.6%
Rash	2/6.7%	1/2.8%	2/2.6%
Other	16/46.7%	30/58.3%	33/60.5%

\* Low Insulin Total AEs > Placebo, p<0.05

+High Insulin Total AEs > Placebo, p<0.10

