### **5.2 Rationale for Primary and Secondary Outcome Measures**

Because no published study has examined the safety of empagliflozin in adults with Alzheimer's disease or in combination with intranasal insulin, the proposed study specifies safety, defined as number of treatment-related adverse events, as the primary outcome..

Regarding secondary measures, in previous studies intranasal insulin acutely improved cognitive performance and affected CSF levels of AD biomarkers as well as MRI measures of vascular integrity (Reger et al. 2008; Craft et al. 2012; Kellar et al. 2021). Thus examining effects on these measures will provide information to be used in the design of a future Phase II trial.

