## **6.0 STUDY OVERVIEW**

The study will consist of a single site, randomized, double-blind trial comparing the effects of 4 weeks of INI (40 International Units q.i.d.), empa (10 mg q.d.) and combined INI and empa compared with placebo on CSF biomarkers and cognition. At study entry, participants will be randomized to one of 4 conditions: INI, empa, INI+empa, placebo. Participants who are cognitively normal but have abnormal elevations of brain amyloid (n=20) or who have MCI or early AD (n=40) will be enrolled. The primary outcome measure will consist of safety (treatment-related serious adverse events). Secondary measures will consist of CSF biomarkers, cognition, and cerebral blood flow. Exploratory measures will include continuous glucose levels and sleep quality as assessed with actigraphy.

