## **15.2 Randomization**

Eligible participants will be randomized on a 1:1 schedule to placebo (insulin diluent; placebo capsule), INI, empa, or INI+empa. Randomization will be stratified by diagnosis (normal, MCI or AD)

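### The only primary analysis, a repeated-measures ANOVA of treatment-related SAE counts with group as a repeated measure, cannot be fitted to four parallel arms, gives no statistic at zero events, and cannot show similarity to placebo

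*Combined protocol and SAP*

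**What the plan says.** The primary hypothesis, in the synopsis and in section 1.1, is that INI, empagliflozin and their combination "will result in safety profiles (number of treatment-related serious adverse events/primary outcome) that are similar to placebo". The synopsis lists the primary outcome as the "number of treatment-related serious adverse events".

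Section 12.0 states how this will be tested, in one sentence: "number of treatment-related SAEs will be subjected to a repeated measures analysis of variance with group and time as the repeated measures". It gives no margin, significance level, confidence interval, list of time points, or rule for zero events. Section 12.1 says that no power calculation was done because this is a proof-of-concept study.

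The design is parallel. Section 6.0: "At study entry, participants will be randomized to one of 4 conditions: INI, empa, INI+empa, placebo". Section 15.2 (Randomization): "Eligible participants will be randomized on a 1:1 schedule to placebo (insulin diluent; placebo capsule), INI, empa, or INI+empa". The total is 60.

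On the expected number of events, section 3.8 reports for the earlier 4-month insulin pilot: "No treatment-related serious adverse events (SAEs) occurred during the study".

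Section 5.2 words the outcome differently: "the proposed study specifies safety, defined as number of treatment-related adverse events, as the primary outcome". Here serious is missing.

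**The concern.** There are four problems, and the first three concern the same sentence in section 12.0.

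1. **Model structure.** A repeated-measures factor needs each participant observed at every level. Here each participant has data at one level of group only.
2. **Zero events.** If group is taken as between-participant, the F ratio has neither numerator nor denominator variance when nobody has an event. For treatment-related SAEs over about 4 weeks in 60 people, that is a realistic result.
3. **Wrong question.** The aim is similarity, but the test is of difference. A non-significant or uncomputable F says nothing about how large an excess risk remains possible.
4. **Outcome definition.** Section 5.2 counts adverse events; the synopsis and sections 1.1, 6.0 and 12.0 count serious ones.

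Section 5.2 makes safety primary because no published study has examined empagliflozin in Alzheimer's disease or combined with intranasal insulin. Section 1.0 says the results will inform a later Phase II trial. That trial needs the risk in each arm and its uncertainty, and the plan as written produces neither.

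**Working it through.** The plan states no figure for this analysis, so there is none to reproduce.

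**Inputs.** N = 60 and four arms (sections 6.0, 6.1). I assume 15 per arm, reading the 1:1 allocation as equal across arms. I also assume at most one event per participant and alpha 0.05. The documents give no SAE rate for this population or combination, so the true rates below are assumed and shown as a range.

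**1. Fit as written.** A repeated-measures ANOVA with group and time both within participant was tried on a 60-participant, four-arm parallel layout with four assumed time points. It stopped with a collinearity error, as the design implies.

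**2. Group as between-participant, on participant totals (df 3 and 56).** With k events in one arm and none elsewhere:

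- Between-group SS = 15[(k/15 − k/60)² + 3(k/60)²]
- Error SS = k − k²/15

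| k | Between SS | Error SS | F | p |
|---|---|---|---|---|
| 0 | 0 | 0 | 0/0 | undefined |
| 1 | 0.050 | 0.933 | 1.00 | 0.400 |
| 2 | 0.200 | 1.733 | 2.15 | 0.104 |
| 3 | 0.450 | 2.400 | 3.50 | 0.021 |
| 4 | 0.800 | 2.933 | 5.09 | 0.0035 |

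**3. Chance of no event in 60**, (1 − r)^60:

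| Assumed rate r, all arms | 0.5% | 1% | 2% | 5% |
|---|---|---|---|---|
| P(no event) | 74% | 55% | 30% | 5% |

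The insulin pilot helps only roughly. It had 36 + 38 = 74 participants on insulin at 20 or 40 IU/day. Section 3.2 describes the higher-dose and placebo arms as "20 International Units INI bid for a total dose of 40 International Units (n=38) or placebo (saline bid, n=30) for 4 months". None received empagliflozin under that protocol. Its 0/74 is compatible with rates up to 1 − 0.025^(1/74) = 4.9%.

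**4. Sensitivity of the repaired test.** Suppose the risk is p in one arm and zero elsewhere. From step 2, p < 0.05 needs k ≥ 3, with k ~ Bin(15, p):

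| True risk in one arm | F significant, P(k ≥ 3) | F undefined, P(k = 0) |
|---|---|---|
| 5% | 3.6% | 46.3% |
| 10% | 18.4% | 20.6% |
| 20% | 60.2% | 3.5% |

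**5. What no events would leave open.** The Clopper-Pearson two-sided 95% upper limit for 0/n is 1 − 0.025^(1/n).

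- n = 15: 21.8%
- n = 30 (two arms pooled): 11.6%
- 0/15 against 0/15: the Wilson upper limit for each arm is 20.4%, so the Newcombe interval for the difference is −20.4 to +20.4 percentage points.

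**6. Validity of the F with sparse events.** Three events all in one arm give F p = 0.021. The exact probability that three events all fall in the same arm is 4·C(15,3)/C(60,3) = 4 × 455/34,220 = 0.053. This is a conditional example, not general inflation. With 400,000 simulated trials and undefined F counted as non-significant, the type I error of the group F is about 0.1% at a common rate of 1%, 2.3% at 5% and 4.2% at 10%. The test is mostly too insensitive.

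No group-by-time p-value is given, because it depends on the number of time points, which section 12.0 does not state.

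**The case against.** The strongest reply is that the factor wording is a slip. Section 3.4 describes the earlier pilot's model with treatment group between participants and time repeated, and that model can be fitted once an event occurs. This is probably right, but it answers only the first problem. The zero-event and similarity problems were assessed on that reading.

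It can also be said that this is a pilot giving preliminary data, that zero events would simply be reported as zero in each arm, and that similar is loose language. The lack of a power calculation is openly justified and is not criticized here. A pilot still needs a primary analysis that can be computed and that bears on its aim. A bare row of zeros, with no upper limit beside it, invites reading 0/15 as evidence of safety.

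Some points stand as limits:

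- The zero-event probabilities rest on assumed rates. If section 5.2 is the intended definition and all adverse events count, those figures do not apply; the factor error and the similarity problem remain.
- The sensitivity and type I figures describe the group effect on participant totals, not a group-by-time analysis.
- A pairwise Fisher test is less sensitive than the omnibus F. Against 0/15 it needs 5 events (p = 0.042; 4 events give 0.0996). With a true risk of 20% in one arm and none in placebo, it reaches p < 0.05 in 16% of trials.
- Newcombe and Fisher can disagree: 4/15 against 0/15 gives an interval of +0.9 to +52.0 points, which excludes zero, although Fisher p is 0.0996.

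The last two points are reasons to put the intervals first and label the p-values descriptive. They are not reasons to keep the ANOVA.

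**Conclusion.** The concern holds, and the plan must be corrected. As written, the sole primary analysis cannot be run. Under its most natural repair it gives no statistic in between 5% and 74% of trials at assumed common rates of 5% down to 0.5%, and it detects a 10% risk confined to one arm in 18.4% of trials. Under no reading can it support similarity to placebo, because there is no margin and no interval. With no events, the data would exclude only risks above about 22% per arm and differences from placebo beyond about 20 percentage points.

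These figures assume 15 per arm, at most one event per participant, and serious events as the outcome. The factor error and the mismatch between test and hypothesis depend on none of these assumptions.

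**What to change.** Replace the primary-aim sentence in section 12.0 with text such as:

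> For each arm, the number and percentage of participants with at least one treatment-related SAE will be reported with a Clopper-Pearson 95% CI, together with the total number of such events. The risk difference of INI, empa and INI+empa versus placebo will be given with a Newcombe 95% CI. Fisher exact p-values are descriptive only. If no event occurs, the same intervals will be reported.

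Also:

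- Reword section 1.1 and the synopsis objective from a claim of similarity to estimating the risk in each arm and the upper limit that the data exclude.
- Reconcile section 5.2 with the synopsis and sections 1.1, 6.0 and 12.0 on whether the outcome is serious or all adverse events.
- State the denominator. Section 8.2 assigns the arm at Visit 2, but study drug is first dispensed at Visit 3 (section 8.3), so randomized and dosed participants may differ.
- State which of the four relatedness categories in section 20.4 count as treatment-related.
- Pooled INI versus no-INI and empa versus no-empa summaries may be added, as supportive only. Pooling can dilute a risk specific to the combination, which the section on combined insulin and empagliflozin safety (under 13.0) raises.

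The cost is wording and trivial analysis work, with no change to visits, sample size or data collection. The outcome summary moves from event counts over time to participants with an event, which is why total events are also listed. The real price is a less favourable safety statement: with no events, the trial can exclude only a risk above about 22% per arm, or about 12% for 30 pooled participants.

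### As written, the conclusion that safety is similar to placebo rests on treatment-related SAEs alone, so an adverse-event excess like the one in the sponsor's 4-month pilot would not count against it

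*Combined protocol and SAP*

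**What the plan says.** The synopsis (Primary Objective) hypothesises that each active regimen "will result in safety profiles (number of treatment-related serious adverse events/primary outcome) that are similar to placebo". Section 1.1 repeats this, and Section 6.0 agrees: "The primary outcome measure will consist of safety (treatment-related serious adverse events").

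Section 12.0 provides one analysis for this aim: the "number of treatment-related SAEs will be subjected to a repeated measures analysis of variance with group and time as the repeated measures". The rest of Section 12.0 covers diagnostic status and efficacy measures: "Secondary analyses will also examine treatment-related differences for other CSF and plasma biomarkers, cognitive scores, and whole brain cerebral blood flow". The secondary outcomes in the synopsis contain no safety variable.

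Section 5.2 differs: "the proposed study specifies safety, defined as number of treatment-related adverse events, as the primary outcome". The word serious is absent there.

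The trial collects more than SAEs. Section 10.1 says that "any occurrence of adverse events will be reviewed and documented", Section 16.1 requires all AEs to be documented whether or not they are related, and Table 4 schedules nasal examinations, vital signs, weight and clinical labs. Section 20.4 is narrower: it records SAEs and only selected AEs, those linked in time to study procedures.

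On the 4-month pilot, Section 3.8 reports both that "No treatment-related serious adverse events (SAEs) occurred during the study" and that "The total AE mean was higher for the low dose group compared with placebo".

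**The concern.** The primary aim is safety, and Section 5.2 justifies this by the lack of published safety data on empagliflozin in Alzheimer's disease or combined with intranasal insulin. The variable that decides the aim is a rare event, and the trial has 60 participants in four arms. The effects that the protocol itself anticipates are mostly not of that kind. The pilot AEs were mostly minor, and Section 13 lists genital infection, volume depletion, frequent urination and rare hypotension for empagliflozin. Such events may be recorded without ever being serious, and nothing in the plan brings them into the comparison with placebo.

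At stake is a statement of similarity, based on few or no events, that Section 1.0 expects to inform a future Phase II trial.

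**Working it through.** **1. Pilot figures (Section 3.8; arm sizes 30, 36 and 38 from Table 1 of Section 3.1).**
- Low dose: difference 1.44 − 0.80 = 0.64; SE = √(0.20² + 0.22²) = 0.297; t = 2.15 on 64 df; p = 0.035, which agrees with the stated 0.04. The 95% CI is 0.64 ± 1.96 × 0.297 = 0.06 to 1.22.
- High dose: difference 0.41; SE = √(0.16² + 0.22²) = 0.272; t = 1.51; p = 0.14 against the stated 0.10. The stated value is not reproduced from the means and SEs alone. Section 3.4 adjusted the efficacy analyses for age, and an adjustment here could explain the gap.
- Table 3 totals give 27/30 = 0.90, 55/36 = 1.53 and 51/38 = 1.34 AEs per person. These are not the stated means (0.80, 1.44, 1.21), but the direction is the same.

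**2. How firm the pilot signal is.**
- Placebo variance over mean is 0.22² × 30 / 0.80 = 1.8, so a Poisson interval would be too narrow. On the log scale, the SE of the low-dose ratio is √((0.20/1.44)² + (0.22/0.80)²) = 0.308. The ratio is 1.44/0.80 = 1.80, 95% CI 0.98 to 3.29. For high dose it is 1.51 (0.83 to 2.75).
- Participants with at least one AE, from the Table 3 percentages: 17/30 on placebo, 26/36 low dose, 26/38 high dose, 52/74 on any insulin. Fisher p against placebo = 0.21, 0.45 and 0.25.
- Nose bleed plus rhinitis: 1 event on placebo, 6 + 8 = 14 on low dose, 3 + 4 = 7 on high dose.

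The pilot therefore suggests an excess of mostly minor events. It does not establish one.

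**3. What the SAE count can show here.** The documents give no rate for this regimen. Assume p per participant, the same in all arms, and 60/4 = 15 per arm.

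| Assumed p | Chance of no event in 60, (1 − p)^60 |
|---|---|
| 0.1% | 94% |
| 0.5% | 74% |
| 1% | 55% |
| 2% | 30% |

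- With no event, the planned analysis of variance has no variance and its F statistic is undefined.
- With 0/15 in an arm, the one-sided 95% upper limit is 1 − 0.05^(1/15) = 18%.
- Against 0/15 on placebo, Fisher's test needs 5/15 to fall below 0.05 (p = 0.042; 4/15 gives 0.10).

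A zero count is thus compatible with a substantial SAE rate and carries no information about non-serious events.

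**4. What an AE comparison would add.** Take the pilot low-dose effect (0.64) and an SD of about 1.2 (0.20 × √36 = 1.20; 0.22 × √30 = 1.20). Power is Φ(0.64 / (1.2 × √(2/n)) − 1.96).
- n = 15 per group: Φ(1.46 − 1.96) = 31%; CI half-width 1.96 × 1.2 × √(2/15) = 0.86.
- n = 30 per group: Φ(2.07 − 1.96) = 54%; half-width 0.61.

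Both powers are optimistic if exposure is 4 weeks rather than the pilot's 4 months. The synopsis and Section 6.0 give 1 month or 4 weeks and Section 1.1 gives 4 months; these need reconciling.

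**The case against.** Several objections have force.

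*Section 5.2 already covers non-serious events.* If it governed, treatment-related non-serious AEs would be in the primary outcome. A reader might infer that such events have no route at all into the conclusion; because of Section 5.2 the documents do not support so absolute a reading. Section 5.2 still requires relatedness, whereas the pilot excess was in total AEs, and it conflicts with the synopsis and Sections 1.1, 6.0 and 12.0.

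*Silence in a short plan does not suppress data.* The pilot's statistical section (3.4) mentions no AE analysis, yet Section 3.8 tabulates and tests AEs by arm. One cannot claim that the pilot would have been reported as similar to placebo, or that AE tables will be withheld here. Section 11.3 also foresees AE analyses by ApoE genotype, and Section 6.0 makes continuous glucose exploratory. What stands is that no comparison of AEs by arm is committed to, and the stated criterion would be met without one.

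*The pilot is a weak guide.* One might scale its upper limit, 1 − 0.05^(1/74) = 4.0%, to 4 weeks (about 0.9%) and conclude that at most 0.9% × 30 = 0.28 events are expected on insulin. That is not a bound. The pilot gave 20 or 40 IU daily with ViaNase; this plan specifies 40 IU four times daily with the Aptar CPS device. Only 23 pilot participants completed the lumbar-puncture sub-study, whereas everyone here is scheduled for two punctures, and Section 20.4 counts relatedness to procedures. Without scaling for time, the same limit gives 4.0% × 30 = 1.2 events.

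*The trial is too small.* True for testing: this is a proof-of-concept study without a power calculation. It argues for estimates with intervals, not for omitting them.

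**Conclusion.** The point holds in limited form. Under the synopsis and Sections 1.1, 6.0 and 12.0, the safety-profile conclusion depends on treatment-related SAEs alone, and a result like the pilot's (none of these, but more AEs on insulin) would satisfy it. This is a stated rule that leads to a weaker conclusion than the collected data allow, not merely a missing detail.

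The size depends on an assumed SAE rate. Over 0.1% to 2% per participant, the chance of no event in the trial runs from 94% to 30%. A reader might infer that zero against zero is the most likely result; that fails at the upper end of the range. Nor do the documents show that intranasal insulin raises AE rates: only the low-dose comparison reached p<0.05, the excess was smaller at the higher dose, and the proportions with at least one AE did not differ significantly.

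The change is a cheap improvement. It would make the safety conclusion better founded but would not give it adequate power.

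**What to change.** 1. Reconcile Section 5.2 with the synopsis and Sections 1.1, 6.0 and 12.0 on whether the primary outcome is restricted to serious events. Reconcile Section 20.4 (selected AEs) with Sections 10.1 and 16.1 (all AEs), so that AE capture is complete.
2. In the synopsis and Section 12.0, name these secondary safety outcomes, reported by arm: participants with at least one treatment-emergent AE; AEs per participant, analysed by a method that allows overdispersion; all-cause SAEs; new nasal-examination abnormality; and change in blood pressure, weight and clinical labs.
3. Give estimates with 95% confidence intervals for each active arm against placebo (15 vs 15). Add the contrasts with versus without intranasal insulin and with versus without empagliflozin (30 vs 30). Label the latter accordingly: each comparator group includes an arm on the other drug, so these are not comparisons with placebo alone.
4. State that the safety-profile conclusion rests on these outcomes together with the SAE count, and that similarity will not be claimed from zero SAEs alone.

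**Cost.** Wording in the synopsis and Section 12.0, and a few tables from assessments already scheduled. It cannot be assumed that no new data are needed: if Section 20.4 reflects actual practice, the AE collection rule must change too. The intervals will be wide, the comparisons descriptive, and the safety statement less clean than a single count.
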